6.2 Study contents

This clinical trial is designed to be a prospective, multi-center, randomized, evaluator-blinded, parallel-controlled, non-inferiority trial. The primary efficacy endpoints are not inferior to the control group. The Biosure Regenesorb Interference Screw and BIOSURE HA Interference Screw are used in the trial and control groups, respectively, to evaluate the safety and effectiveness of the investigational medical device Biosure Regenesorb Interference Screw in clinical repair or reconstruction of knee cruciate ligament rupture or tear.

The subjects complying with the criteria for inclusion in this clinical trial will receive 24-month follow-up after being treated with the investigational product or the control product. The following endpoints will be recorded and evaluated: Lysholm score, IKDC score, Drawer test, Lachman test and imaging evaluation results at the follow-up visit at month 6, 12 and 24 after the operation, respectively, incidence and frequency of ADEs, AEs, and device deficiency throughout the trial and reoperation rate.

7 Background of Clinical Trial

The knee becomes one of the most injured joints due to its anatomical structure and particular function in human body. According to the statistics, there are 200,000 ACL rupture cases per year in the United States, including 100,000 requiring ACL reconstruction. An epidemiological investigation in sport injury showed that the total incidence of ACL injury is 0.47% in China. PCL injury are relatively infrequent. As reported in foreign literature, PCL injury has an incidence of 3% in the common population and account for 20% of knee ligament injury. No similar reports are found in China.

The ACL femoral attachment, located at the posterior part of the medial side of the lateral femoral

Confidential and Proprietary

This document contains confidential and proprietary information on Smith & Nephew PLC and Smith & Nephew, Inc. and is only available to Smith & Nephew and its manufacturers. Without prior written approval of Smith & Nephew, the content cannot be replicated, printed totally/partially or disclosed in any other way, and anyone must use it as per the requirements, either expressed or implied by Smith & Nephew.

Study Protocol - Device	Smith+Nephew

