10.1.4.4 Criteria and procedures for withdrawal/termination of study

Participation in the study is voluntary and subjects may drop out at any time point in the study. Any subjects who have not completed the study should make every effort to complete the final evaluation. The reason for withdrawal must be recorded in the original document and the corresponding case report form (CRF). After the subject withdraws from the study, there is no need to replace him/her or continue follow-up.

Investigators may also choose subjects to withdraw from the study for reasons including but not limited to:

- Serious Adverse Event
- Investigators decide subjects to withdraw for safety reasons.
- The subjects do not accept the investigational device implantation during the operation
- The subjects do not comply with follow-up
- Subjects are lost to follow-up

When investigators decide subjects to withdraw, the relevant reasons should be recorded in the

Confidential and Proprietary

This document contains confidential and proprietary information on Smith & Nephew PLC and Smith & Nephew, Inc. and is only available to Smith & Nephew and its manufacturers. Without prior written approval of Smith & Nephew, the content cannot be replicated, printed totally/partially or disclosed in any other way, and anyone must use it as per the requirements, either expressed or implied by Smith & Nephew.

Study Protocol - Device	Smith+Nephew
A Prospective, Multi-center, Randomized Clinical Study to Evaluate the Safety and Effectiveness of Biosure Regenesorb Interference Screw in Arthroscopic Reconstruction of Cruciate Ligaments in Chinese Patients	Study No.: BIOSURE RG.SMD.PMA.2019.01
	Version: V2.0/July 3rd, 2020
	Page 29 of 74

original document and the corresponding case report form (CRF).

This study may be temporarily suspended or prematurely terminated if there is sufficient reasonable cause. Written notification, documenting the reason for study suspension or termination, will be provided by the suspending or terminating party to other parties (investigator, Ethics Committee, Sponsor and regulatory authorities). If the study is prematurely terminated or suspended, the investigator will promptly inform the Ethics Committee and the GCP office and will provide the reason(s) for the termination or suspension. Circumstances that may need termination or suspension include, but are not limited to:

- Determination of unexpected, significant, or unacceptable risk to participants

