12.9 Selection criteria and justification of subjects included in the analysis

12.9.1 Full Analysis Set (FAS)

Confidential and Proprietary

This document contains confidential and proprietary information on Smith & Nephew PLC and Smith & Nephew, Inc. and is only available to Smith & Nephew and its manufacturers. Without prior written approval of Smith & Nephew, the content cannot be replicated, printed totally/partially or disclosed in any other way, and anyone must use it as per the requirements, either expressed or implied by Smith & Nephew.

Study Protocol - Device	Smith+Nephew
A Prospective, Multi-center, Randomized Clinical Study to Evaluate the Safety and Effectiveness of Biosure Regenesorb Interference Screw in Arthroscopic Reconstruction of Cruciate Ligaments in Chinese Patients	Study No.: BIOSURE RG.SMD.PMA.2019.01
	Version: V2.0/July 3rd, 2020
	Page 49 of 74

Full Analysis Set (FAS): According to the basic principle of Intention To Treat (ITT), all subjects who are randomized in the trial and have at least one effectiveness evaluation are included in the Full Analysis Set. The Last Observation Carried Forward (LOCF) is used for analysis when the primary efficacy endpoint is missing.

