16.1 Definition

An adverse event is defined as any untoward medical occurrence in a clinical investigation in which a subject is administered a study device and which does not necessarily have a causal relationship with the device. An adverse event can therefore be any unfavorable and unintended sign (including an abnormal laboratory finding), symptom, or disease temporally associated with the use of study device, whether or not related to the study device.

Any events that occur newly or deteriorate in severity and frequency as compared with baseline conditions, or abnormal results found in the process of diagnosis, including abnormal laboratory findings, are included herein.

Note: The Sponsor collects the information on adverse events when the subjects sign the informed consent form.

The following are specific definitions of adverse events:

AE Adverse event - any untoward medical occurrence in a subject, regardless if there is a relationship between the AE and the device.

SAE Serious Adverse Event - an adverse event that:

A Serious Adverse Event is any AE that results in a death or a serious deterioration in the health of the subject during the clinical trial, including a life-threatening illness or injury, a permanent impairment of a body structure or a body function, in-patient hospitalization or prolongation of existing hospitalization, medical or surgical intervention to prevent permanent impairment of a body structure or a body function; or results in fetal distress, foetal death or congenital abnormality, congenital anomaly, etc.

ADE Adverse Device Effect – any untoward and unintended response to a medical device (This definition includes any event that is a result of a user error).

SADE Serious Adverse Device Effect – An adverse effect that has resulted in any of the consequences characteristic of a serious adverse event

UADE Unanticipated Adverse Device Effect - An “unanticipated adverse device effect” (UADE) is defined as any serious adverse effect on health or safety or any life-threatening problem or death caused by or associated with this device which was not previously identified in nature, severity, or

Confidential and Proprietary

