The administrative department of medical device clinical trials shall send written reports to corresponding EC, the food and drug administration of the concerned province or autonomous region or municipality directly under the central government, and the competent authority of health and family planning within 24h. Regarding adverse events of death, study sites and investigators should provide all required data to the corresponding Ethics Committees and Sponsor.

Details of all adverse events or device deficiency must be recorded on the adverse event/device deficiency forms provided and faxed/e-mailed to the contact of Sponsor where possible at the time of reporting. Please keep the fax report or print an email as a record of the time limit. The contact details are shown in the Section “1. Sponsor Information” of the protocol.

The Investigator must submit a detailed report that will identify the description of symptoms, classification of the event, date of onset, severity, treatment, and outcome. Supporting medical records may be obtained as an adjunct to an adverse event report and placed in the subject’s study file.

During the clinical study, all serious and non-serious adverse events should be followed up to determine the final outcome.

All SAEs, which haven’t been resolved at the end of the study or when the subjects withdraw prematurely from the study, must be followed up until one of the followings is achieved:

- The event is resolved
- Achieve stable state
- Reasonable explanation is provided
- Lost to follow-up or death
- The event restores to the baseline level (if the baseline value is available)
- When it is impossible to obtain more information (the patient or medical staff refuses to provide more information, and there is evidence showing that the patient is still lost to follow-up after the medical staff tries his/her best)

Once a subject has completed the study, the investigator should follow up for outcomes on all AEs

Confidential and Proprietary

This document contains confidential and proprietary information on Smith & Nephew PLC and Smith & Nephew, Inc. and is only available to Smith & Nephew and its manufacturers. Without prior written approval of Smith & Nephew, the content cannot be replicated, printed totally/partially or disclosed in any other way, and anyone must use it as per the requirements, either expressed or implied by Smith & Nephew.

Study Protocol - Device	Smith+Nephew

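### Section 10.1.4.4 does not separate stopping study procedures from stopping data collection, so a device failure withdrawn by the investigator can lose its month-12 Lysholm score and later safety data

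*Combined protocol and SAP*

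**What the plan says.** **Withdrawal (10.1.4.4).** The first paragraph deals with subjects who drop out voluntarily. It asks for an exit assessment: "Any subjects who have not completed the study should make every effort to complete the final evaluation". It does not define the timing or content of that assessment. The paragraph ends: "After the subject withdraws from the study, there is no need to replace him/her or continue follow-up".

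A new paragraph then begins "Investigators may also choose subjects to withdraw from the study for reasons including but not limited to". The reasons listed include a serious adverse event, safety reasons, and not complying with follow-up. None is limited to the time before implantation.

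**What counts as serious (16.1).** The definition includes "in-patient hospitalization or prolongation of existing hospitalization, medical or surgical intervention to prevent permanent impairment of a body structure or a body function".

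**Follow-up of SAEs (16.3.1).** SAEs still open "when the subjects withdraw prematurely from the study, must be followed up until one of the followings is achieved"; this also applies to SAEs still open when the study closes. Resolution and a stable state are among the end points listed.

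**Analysis sets (12.1.3 and 12.9).** The primary evaluation uses both the full analysis set (FAS) and the per-protocol set (PPS). For the FAS, "all subjects who are randomized in the trial and have at least one effectiveness evaluation are included in the Full Analysis Set", and "The Last Observation Carried Forward (LOCF) is used for analysis when the primary efficacy endpoint is missing". The PPS is limited to subjects who complete the trial without a serious protocol violation.

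**Safety (6.2).** The plan evaluates "incidence and frequency of ADEs, AEs, and device deficiency throughout the trial and reoperation rate".

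**The concern.** The treatment is a single implantation. Withdrawing a subject after surgery does not stop the treatment; it stops study procedures and, as the text stands, may stop data collection too. A screw or graft failure that leads to hospital admission or further surgery can meet the SAE definition, so a listed reason for withdrawal can be the outcome of interest itself.

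The investigator decides on withdrawal. Section 10.1.3.2 states blinding only for the independent rater. Section 10.1.4.5 requires at least two documented phone contacts and a certified letter before a subject is declared lost, whereas 10.1.4.4 sets no such step before withdrawal for not complying with follow-up.

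Two things are at stake. One is the month-12 Lysholm comparison, where failures lost unevenly between the arms bias the difference. The other is the record of adverse events and reoperations to month 24, the period that 10.1.2 sets aside for long-term performance and absorbability.

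**Working it through.** **1. The plan's own sample size.** Inputs from 12.2.1: margin 5, spread 9, true difference 0, one-sided alpha 0.025, power 80%.

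n per group = 2 × (1.960 + 0.842)² × 9² / 5² = 50.9, so 51. With 20% drop-out, 51 / 0.8 = 63.75, so 64. Both match the plan. They match only if 9 is the standard deviation; read as a variance, as the text calls it, 9 gives 6 per group.

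At 70 per group less 20%, 56 remain and power is 83.6% (normal approximation). The loss of numbers is therefore covered. The allowance does nothing about bias when the reason for loss is related to the outcome.

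**2. What happens to a failure withdrawn before month 12.** The schedule has a Lysholm score before surgery and then at months 6, 12 and 24.

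| Case | PPS | FAS |
|---|---|---|
| Failure before month 6, no exit score | Out | Out, or carried at the pre-operative score; 12.9.1 does not say whether that score qualifies |
| Failure after month 6, no exit score | Out | Carried at the month-6 score, taken before the failure |
| Exit Lysholm taken after the failure | Out | Exit score carried forward, so the failure shows, but not as a month-12 observation |

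**3. Safety record.** Under 16.3.1 the unresolved SAE is followed to an outcome, so a reoperation that is that SAE, or part of its course, should be recorded. No rule covers a new event or a reoperation after that SAE closes. The safety set in 12.9.3 has no completion requirement, so the subject stays in the denominator while later events can be missed.

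**4. Size in the means.** Let D be the Lysholm deficit of a failed knee, and k_T and k_C the failures removed from each 70-subject arm.

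Shift in one arm's mean = k × D / 70. Shift in the difference = (k_T − k_C) × D / 70.

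The documents give no D. I assume 25 to 45. From the middle of the good band in 10.1.5.1 (84 to 94, so 89) this gives scores of 64 to 44, all in the poor band (below 65).

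- One net failure: 25/70 = 0.36 to 45/70 = 0.64 points, or 7% to 13% of the margin.
- Five removed from the trial arm against three from control: 2 × 25/70 = 0.71 to 2 × 45/70 = 1.29 points, or 14% to 26% of the margin.
- Five from the trial arm and none from control: 1.79 to 3.21 points, or 36% to 64%. This is the one-sided extreme.
- Equal numbers removed: about zero.

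These shifts apply where the subject is dropped: the PPS, or the FAS with no qualifying score. They do not describe the cases handled by carrying a score forward.

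**5. Effect on the error rate, as illustration.** Simulation with 70 per arm, SD 9 and 10,000 runs per scenario. The true all-subject difference is exactly −5, and success means that the lower limit of the two-sided 95% t-interval is above −5. Failure rates and deficits are assumptions, and every scenario has more failures in the trial arm.

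| Failures, trial vs control | Deficit | None dropped | Half dropped | All dropped |
|---|---|---|---|---|
| 5% vs 2% | 20 | 2.6% | 3.6% | 5.9% |
| 8% vs 3% | 30 | 2.9% | 6.8% | 16.3% |
| 10% vs 2% | 30 | 2.6% | 9.6% | 32.7% |

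**The case against.** The best defence is the order of the text. The sentence releasing sites from follow-up closes the paragraph on voluntary drop-out, where it is ordinary, and the investigator's list comes afterwards. A reader might infer that the protocol states outright that a subject withdrawn for an SAE is not followed. It does not: applying the sentence to that subject is one reading of unclear text, and 16.3.1 points the other way for the open SAE. What stands against the defence is that the sentence is worded for withdrawal in general, and nothing in 10.1.4.4 exempts withdrawal by the investigator.

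A reader might also infer that failures vanish from both the primary comparison and the reoperation count. That goes too far. The triggering SAE is reportable and must be followed, the safety set keeps the subject, and the FAS keeps anyone with a qualifying score. An exit Lysholm would carry a poor score forward, and a carried pre-operative score would probably count against the arm. Certain removal is limited to the PPS. Even so, no observed month-12 score is secured in any of these cases.

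Nor is the direction fixed. The documents give no failure rate, withdrawal fraction or imbalance between arms. Removal from control alone would bias against the investigational screw.

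Finally, withdrawal can have a legitimate purpose: the schedule includes X-ray, CT and MRI at months 6, 12 and 24, and an investigator may have safety grounds to stop them. This defeats any proposal to strike SAEs or safety from the list of reasons. It does not justify stopping a questionnaire score or a telephone enquiry.

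**Conclusion.** The point holds in limited form. Section 10.1.4.4 does not distinguish stopping procedures from stopping data collection, leaves the final evaluation undefined, and must be reconciled with 16.3.1. A site that follows it may stop collecting the month-12 Lysholm score and later adverse event and reoperation data for reasons tied to the outcome.

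The consequence is certain for the PPS. In the FAS it is the loss of an observed score, with a replacement that may hide the failure or may penalise it. For safety it is a possible undercount of new events after the triggering SAE closes.

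The bias in the difference is about 0.36 to 0.64 points per net failure removed. This rests on an assumed deficit of 25 to 45 points and on an imbalance between arms that the documents do not give. They do not support a statement that the result will favour the investigational screw. This is a cheap improvement, best made in the protocol, because outcomes not collected cannot be recovered at analysis.

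**What to change.** Keep the investigator's discretion to stop study procedures, and replace the no-follow-up sentence in 10.1.4.4 with wording such as:

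> Subjects who stop study procedures or are withdrawn by the investigator are not replaced. Unless the subject withdraws consent to data collection, the month-12 Lysholm score (remotely if needed) and adverse event and reoperation status to month 24 (by telephone if needed) are still collected. The observed month-12 score is used in the FAS in place of LOCF.

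Then:

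- Reconcile this text with 16.3.1.
- State in 12.9.1 whether the pre-operative score qualifies a subject for the FAS.
- State in 12.9.2 whether a subject scored at month 12 in this way counts as having completed the trial.

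The means already exist: footnote (8) of the follow-up schedule allows remote Lysholm scoring, and 10.2.2.6 already collects adverse events and the need for reoperation by telephone. The cost is an amendment to the wording and a few retained contacts. The downside for the sponsor is that some poor scores and late events enter the results.

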10.1.4.6 Time of enrollment

The study enrollment can be started only after the Ethics Committee has approved and signed a clinical trial agreement at each site. Before the enrollment, the relevant procedures and requirements should be completed according to the regulations of relevant departments. The competitive enrollment is taken in the study with a preliminarily estimated time of 12 months. The enrollment time can be adjusted according to the actual situation.

Subjects who have completed the informed consent form and have been assigned a random number are considered to be enrolled.

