10.2.2 Study procedures

10.2.2.1 Evaluation before enrollment in the study

Prior to initiating any study-related activities on a subject, sites must first perform the following pre-study activities:

- Informed consent must be obtained from each subject entering the study using the EC-approved consent form. Informed consent must be obtained prior to any study activity.
- Inclusion and exclusion criteria will be carefully reviewed to verify subject eligibility.
- All combination drugs associated with AEs or SAEs are recorded after the subject signs the ICF.
- The subject enrollment time is the moment when the device is implanted.

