This document contains confidential and proprietary information on Smith & Nephew PLC and Smith & Nephew, Inc. and is only available to Smith & Nephew and its manufacturers. Without prior written approval of Smith & Nephew, the content cannot be replicated, printed totally/partially or disclosed in any other way, and anyone must use it as per the requirements, either expressed or implied by Smith & Nephew.

Study Protocol - Device	Smith+Nephew
A Prospective, Multi-center, Randomized Clinical Study to Evaluate the Safety and Effectiveness of Biosure Regenesorb Interference Screw in Arthroscopic Reconstruction of Cruciate Ligaments in Chinese Patients	Study No.: BIOSURE RG.SMD.PMA.2019.01
	Version: V2.0/July 3rd, 2020
	Page 38 of 74

If device replacement/repair is required in the initial operation, the investigators will need to replace/repair the device according to the conventional medical device replacement/repair method (e.g., other safe fixation methods).

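### A randomised subject can be withdrawn at surgery for not accepting the investigational device and then not followed, and the two definitions of enrolment leave unclear whether that subject counts toward the 140

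*Combined protocol and SAP*

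**What the plan says.** **Withdrawal.** Section 10.1.4.4 opens its list of investigator-initiated withdrawals with "Investigators may also choose subjects to withdraw from the study for reasons including but not limited to". One item is "The subjects do not accept the investigational device implantation during the operation". The same section says "After the subject withdraws from the study, there is no need to replace him/her or continue follow-up", but also "Any subjects who have not completed the study should make every effort to complete the final evaluation". It does not say which visit the final evaluation is.

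**Device problems at surgery.** Section 10.2.2.4 says "If device replacement/repair is required in the initial operation, the investigators will need to replace/repair the device" by conventional means, which include other ways of fixing the graft. It speaks of the device generally, so it covers both arms, and it is silent on whether the subject remains in the study.

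**Enrolment.** Section 10.1.4.6: "Subjects who have completed the informed consent form and have been assigned a random number are considered to be enrolled". Section 10.2.2.1: "The subject enrollment time is the moment when the device is implanted". Section 10.1.3.7 keeps recruitment open until 140 subjects are reached.

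**Analysis sets.** Section 12.9.1 invokes intention to treat and says "all subjects who are randomized in the trial and have at least one effectiveness evaluation are included in the Full Analysis Set", with last observation carried forward (LOCF) for a missing primary endpoint. The per-protocol set (12.9.2) holds subjects who complete the trial without serious violation. The safety set (12.9.3) is defined by random assignment to the investigational device.

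**Blinding.** Section 10.1.3.2 blinds an independent rater at each site and no one else. Note 7 to the follow-up schedule places randomisation after consent and before anaesthesia.

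**The concern.** Whether the allocated screw is implanted is known only after randomisation, is tied to the device, and is decided in the operating room by someone not described as blinded. A rule that lets such subjects be withdrawn and not followed makes the analysed groups depend on what happened to the device. That is the selection which an intention-to-treat analysis is meant to prevent.

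Three features aggravate it:

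- The listed ground names the investigational device. Section 6.2 and the synopsis use that term for Regenesorb and give BIOSURE HA a separate name, so the text gives investigators an explicit prompt for one arm and none for the other.
- Replacement of a screw at the initial operation is foreseen, and section 16.3.5 gives screw breakage as an example of a device deficiency. The study status of such a subject is left open.
- If a site counts enrolment from implantation, a randomised subject without an implant may not count toward the 140, and recruitment may continue past him or her. That would act as a replacement, although 10.1.4.4 sees no need for one.

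At stake is the comparability of the two arms on the 12-month Lysholm score, in a non-inferiority trial with a margin of 5 points.

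**Working it through.** **1. The plan's own figure.** Inputs from 12.2.1: margin 5, spread 9, true difference 0, one-sided alpha 0.025, power 0.80. n = 2(1.960 + 0.842)² × 9² / 5² = 50.9, so 51 per group. 51/0.8 = 63.75, so 64 per group and 128 in total; adding 12 gives 140, or 70 per group. This reproduces the plan. It works only with 9 as the standard deviation: the plan calls 9 a variance, which would give 5.7, so 6 per group. SD 9 is used below. The point itself does not depend on this figure.

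**2. Where a subject withdrawn at surgery goes.** Such a subject has a pre-operative Lysholm score (follow-up schedule and 10.2.2.2) and no month-6 or month-12 score.

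- *Per-protocol set:* out, because the trial was not completed.
- *Full analysis set, reading A:* the required effectiveness evaluation must be post-operative. The subject is out.
- *Full analysis set, reading B:* the pre-operative score counts. Section 12.9.1 does not exclude this. The subject is in, and LOCF (12.7, 12.9.1) supplies the pre-operative score as the month-12 value.

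**3. Size under reading A.** Suppose k of N subjects in one arm are removed and would have scored D points below the rest of that arm. With everyone included, the arm mean is x − kD/N; after removal it is x. The arm gains kD/N. The documents give neither k nor D. Assume N = 70, D = 15 and no removals in the other arm:

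| k | shift in points | share of margin 5 |
|---|---|---|
| 2 | 2 × 15/70 = 0.43 | 9% |
| 4 | 4 × 15/70 = 0.86 | 17% |
| 6 | 6 × 15/70 = 1.29 | 26% |

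If the removals are in the Regenesorb arm and the true difference sits at −5, the one-sided error is 1 − Φ(1.96 − shift/SE), with SE = 9√(1/70 + 1/(70 − k)). For k = 4, SE = 1.544 and the error is 1 − Φ(1.96 − 0.857/1.544) = 0.080 instead of 0.025. For k = 2 it is 0.046, and for k = 6 it is 0.128. The result is sensitive to D: one removal with D = 10 gives 0.14 points and 0.031; four with D = 20 give 1.14 points and 0.111.

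**4. Offset from the control arm.** If both arms lose subjects with the same deficit, the net shift is (k_T − k_C) × D/N. Four against two gives 2 × 15/70 = 0.43 points; four against four gives zero.

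**5. Direction under reading B.** If the carried-forward score lies B points below what the subject would have scored at month 12, the arm mean falls by kB/N. With B = 15, also an assumption, the shifts are −0.43, −0.86 and −1.29 for k = 2, 4 and 6: the same sizes with the opposite sign.

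**6. Enrolment.** Sections 10.1.4.6 and 10.2.2.1 cannot both hold for a subject who is randomised but not implanted. The first counts that subject and the second does not. The analysis sets are defined from randomisation, so the conflict bears mainly on the count of 140 and on when recruitment stops.

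**The case against.** The strongest reply is that the text is loose rather than one-sided, and much of that stands.

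- A reader might infer that only Regenesorb subjects can be withdrawn for non-receipt while equivalent control subjects must stay. The documents do not support this. The list is permissive and open-ended, so a BIOSURE HA subject can be withdrawn too. The safety set in 12.9.3 also names only the investigational device. Read literally it would leave the control arm out of the safety analysis, so the term may simply mean the study screw.
- A reader might equate the ground with a screw that breaks or will not seat. The item speaks of not accepting implantation, which could mean refusal or non-receipt, and the protocol never links a failed insertion in 10.2.2.4 to withdrawal. If it means refusal, no rule can override the right to withdraw consent.
- A reader might infer a bias in favour of the new screw. Reading B and LOCF point the other way.
- A reader might infer that failures vanish from the device-deficiency count. Sections 10.2.2.3 and 16.3.5 collect deficiencies during the operation, so that is speculative.
- The assumed deficit has no source in the protocol. The background section says stability does not vary with screw material or with single or combined use.

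What the reply does not remove is the discretion itself. On any reading, a randomised subject can be withdrawn for a device-related reason by someone not described as blinded and then not followed. The request to attempt a final evaluation softens this but contradicts the adjacent statement on follow-up.

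**Conclusion.** The point holds as a defect in the rules, not as a demonstrated bias. Section 10.1.4.4 permits device-related withdrawal after randomisation without required follow-up, in words that name one device. Section 10.2.2.4 leaves the status of a subject with a replaced device undefined, and the two enrolment definitions conflict. This is at odds with the intention-to-treat principle in 12.9.1.

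Neither the direction nor the size of any effect can be established from the documents. The 0.43 to 1.29 points (9% to 26% of the margin) rest on three assumptions: 2 to 6 of 70 removed, a 15-point deficit, and no control removals. The sign reverses if pre-operative scores are carried forward, and the shift cancels if the arms lose similar subjects equally. One or two removals would matter little unless the deficit is large; several in one arm could matter. The change is worth making before database lock because it is cheap and removes the dependence on unstated readings.

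**What to change.** 1. In 10.1.4.4, remove non-receipt of the device as a withdrawal ground, and reconcile the statement on follow-up with the request for a final evaluation.
2. Reconcile 10.1.4.4, 10.2.2.4 and 12.9.3 with one rule for both arms. A randomised subject who does not receive the allocated screw, or has it replaced at the initial operation, is followed through months 12 and 24 unless consent is withdrawn, is analysed in the full analysis set as randomised, and is recorded as a device deficiency where the device is the cause. The choice of replacement fixation is a surgical matter and is not touched.
3. Delete the sentence in 10.2.2.1 that dates enrolment from implantation, so that the count of 140 runs from the random number as in 10.1.4.6.
4. Add one eCRF item: allocated screw implanted (yes, no or replaced), with the reason.

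Once these subjects have an observed month-12 score, the choice between readings A and B no longer affects them. The cost is a few wording changes and one eCRF item, with no extra subjects. The downside is that a few subjects without the allocated screw remain in the full analysis set. In a non-inferiority trial this can dilute a true difference between the screws, so the per-protocol analysis should be read beside it, as the plan already provides.
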